8.7 Efficacy Analyses

The efficacy analysis will be based on full analysis set.

8.7.1.1 Best Overall Response

Best Overall Response (BOR) is defined as the best overall response recorded from the start of treatment until disease progression or initiation of alternative therapy or end of study. A summary of subjects achieving a best overall response in a given category (CR, PR, SD, PD, NE, and Missing) will be provided.

In phase II, BOR will be summarized by investigator.

8.7.1.2 Analysis of Primary Efficacy Endpoint

Objective response rate (ORR) will be calculated and summarized by treatment group, along with the 95% of confidence interval calculated by the Clopper-Pearson method.

8.7.1.3 Analysis of Secondary Efficacy Endpoint

If the sample size or the number of responders allow for meaningful interpretation, Kaplan-Meier method will be used to analyze the duration of response (DoR), the progression-free survival (PFS), time to response (TTR) and time to progression (TTP) for each tumor type, genetic mutation and other factors required by sponsor. If possible, a 95% of confidence interval band should be provided for each estimate.

For all the time-to-event endpoints (DoR, PFS, TTR and TTP), the survival curve will be estimated by the Kaplan-Meier estimate, and the first percentile, the median survival, the third percentile and their 95% CI will be provided.

For Time to Response (TTR) and Duration of Response (DoR), only subjects with BOR is CR/PR during the study treatment will be calculated.

DCR and 1-year overall survival (OS) rate will be estimated and analyzed by the same methods as those in ORR.

The listing of all the time-to-event endpoints will be provided.

See Appendix , B, C and E for detailed rule of Censor date for PFS and other time-to-event endpoints.

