10.2 Appendix B Censor rule for TTR

No.	Situation	Events or Censor	Analysis date*
1	CR, PR before PD, Death, alternative anti-cancer therapy or missed two consecutive assessment.	Events	First CR, PR date
2	No CR/PR/ alternative anti-cancer therapy/ missed two consecutive assessment/PD/Death	Censor	Last assessment date
3	No CR/PR, have PD or Death	Censor	First date of PD or Death
4	No CR/PR before alternative anti-cancer therapy	Censor	Last assessment date before initiating alternative anti-cancer therapy
5	No CR/PR before missed two consecutive assessment	Censor	Last assessment date before the missed two consecutive assessment

* If there are multiple assessment date on one tumor assessment, choose the earliest assessment date when overall response is PD, and choose the latest assessment date when overall response is CR/PR/SD.

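### SAP 8.7.1.3 limits time to response to responders, but the Appendix B it refers to also censors non-responders, and nothing says which rule governs

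*SAP*

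**What the plan says.** SAP 8.7.1.3 sets the population in one sentence: for TTR and duration of response, "only subjects with BOR is CR/PR during the study treatment will be calculated". The same section fixes the estimator: "For all the time-to-event endpoints (DoR, PFS, TTR and TTP), the survival curve will be estimated by the Kaplan-Meier estimate", with quartiles, median and 95% confidence intervals. It closes with a cross-reference: "See Appendix , B, C and E for detailed rule of Censor date for PFS and other time-to-event endpoints".

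SAP Appendix B has five rows. Row 1 is the event: a CR or PR that comes before progression, death, new anti-cancer therapy or two consecutive missed assessments. The other four rows censor:

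- Row 2: no response and none of the other happenings; censored at the last assessment.
- Row 3: "No CR/PR, have PD or Death"; censored at "First date of PD or Death".
- Row 4: "No CR/PR before alternative anti-cancer therapy"; censored at the last assessment before that therapy.
- Row 5: "No CR/PR before missed two consecutive assessment"; censored at the last assessment before the gap.

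Other sections do not settle the population. SAP 8.7 puts efficacy on the full analysis set (all treated patients). SAP Appendix E defines TTR from first treatment day to first CR or PR and names no population. Protocol 10.6.3 plans Kaplan-Meier for TTR without restricting it to responders. SAP 8.12, which lists departures from the protocol, does not mention TTR.

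**The concern.** The body text and the appendix imply different analysis populations for one named endpoint. Two programmers working from this SAP could each follow a written rule and report different medians.

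The all-treated version has a further problem. Under SAP 8.7.1.1, best overall response is counted only up to progression, new therapy or end of study. SAP Appendix E counts an objective response only if it precedes progression. A patient who has progressed or died can therefore no longer become a responder. Kaplan-Meier censoring at that date treats the patient as if he or she would go on to respond at the same rate as those still at risk. As an estimate of the cumulative probability of response, one minus Kaplan-Meier is then too high.

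**Working it through.** **Which rows can reach a responder.** Take a patient whose best overall response is CR or PR.

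- Rows 2 and 3 require no CR or PR, so they cannot apply.
- Row 4 requires no response before new therapy. Best overall response stops counting at new therapy, so row 4 cannot apply either.
- Row 5 can apply. The best overall response definition has no missed-visit limit, so a patient whose first CR or PR follows two missed assessments is a responder under 8.7.1.3. That patient fails the row 1 event condition and is censored by row 5.

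Rows 2 to 4 therefore have work to do only if non-responders are in the analysis.

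**Inputs for the size.** The documents give no TTR figure to reproduce and no progression or death rate. They do give a response rate of 0.16 under the alternative and at most 36 patients in each of cohorts 1 and 2 (SAP 3.2), 21-day cycles (protocol 6.1) and assessments every two cycles, hence every 6 weeks (protocol 7.2.5). At 0.16 the exact two-stage binomial calculation gives power 0.8195, against the stated 0.8201. Expected responders at full enrolment are 36 × 0.16 = 5.76. The 8.7.1.3 analysis would rest on about 6 patients per cohort, and the Appendix B analysis on up to 36.

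**Scenario 1 (assumed).** Response rate 16%. Responses fall 70% at week 6 (0.112 of all patients) and 30% at week 12 (0.048). The 84% who do not respond have exponential time to progression with median 10 weeks, so the fraction free of progression is 2^(-0.6) = 0.6598 at week 6 and 2^(-1.2) = 0.4353 at week 12.

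*Progression dated at 6-weekly visits, with tied censorings after events:*
- Week 6: all at risk; factor 1 - 0.112/1 = 0.8880.
- Week 12: at risk 0.048 + 0.84 × 0.6598 = 0.6022; factor 1 - 0.048/0.6022 = 0.9203.
- One minus Kaplan-Meier = 1 - 0.8880 × 0.9203 = **18.3%**.

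*Continuous progression dates:*
- Week 6: at risk 0.16 + 0.84 × 0.6598 = 0.7142; factor 1 - 0.112/0.7142 = 0.8432.
- Week 12: at risk 0.048 + 0.84 × 0.4353 = 0.4136; factor 1 - 0.048/0.4136 = 0.8840.
- One minus Kaplan-Meier = 1 - 0.8432 × 0.8840 = **25.5%**.

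The true cumulative response is 16% in both cases. The all-treated curve never falls to 0.5, so its median is not reached. The responders-only median is 6 weeks.

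**Scenario 2 (assumed), varying the rate.** Let h be a constant probability per 6-week visit of leaving the state of no response and no progression, with a share R = 0.16 of exits being responses. At week 24 (4 visits):

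- cumulative incidence = R × [1 - (1 - h)^4];
- one minus Kaplan-Meier under Appendix B = 1 - (1 - R × h)^4;
- the median is the first visit k with (1 - R × h)^k ≤ 0.5 for all treated, or (1 - h)^k ≤ 0.5 for responders only.

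| h | Cumulative incidence, week 24 | Appendix B 1 - KM, week 24 | Median, Appendix B | Median, responders only |
|---|---|---|---|---|
| 0.20 | 9.4% | 12.2% | 132 weeks | 24 weeks |
| 0.35 | 13.1% | 20.6% | 78 weeks | 12 weeks |
| 0.50 | 15.0% | 28.4% | 54 weeks | 6 weeks |
| 0.70 | 15.9% | 37.8% | 36 weeks | 6 weeks |

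The week-24 excess runs from 12.2 - 9.4 = 2.8 to 37.8 - 15.9 = 21.9 percentage points. The direction is the same throughout. The size follows the assumed rate.

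**The case against.** The best defence is that 8.7.1.3 is the only sentence that names a TTR population, and it is specific where the full-analysis-set rule in 8.7 is general. Appendix B calls itself a censoring rule, and 8.7.1.3 refers to it only for censoring dates. Read that way, 8.7.1.3 selects the patients and Appendix B dates them, so non-responders never enter. This is a fair reading. It means that the bias is conditional on Appendix B governing. It does not remove the inconsistency, because the SAP never states that order of precedence and three of the five rows are left with nobody to apply to.

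It is also true that response probability is to be reported as ORR with a Clopper-Pearson interval (SAP 8.7.1.2). No section uses the TTR curve as a response rate, so the percentages above show distortion of the curve and are not planned results.

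A reader might infer two stronger things:

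- That the planned TTR analysis is biased as it stands. The documents do not support this, since under 8.7.1.3 the bias is absent.
- That no responder is ever censored, so that rows 2 to 5 can all go. Row 5 can censor a responder whose first response follows two missed assessments. Deleting it would leave that patient failing row 1 with no rule in its place.

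**Conclusion.** The contradiction stands: the text and the appendix it cites define TTR on different patients, and nothing chooses between them. Under the all-treated reading, censoring at progression or death inflates the curve and gives a median of a different kind from the responders-only one. Only the direction of that bias is firm. In scenario 1 the excess over 16% is 2.3 or 9.5 percentage points, depending solely on how progression is dated, so no single figure should be quoted as the effect.

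The importance is minor. TTR is secondary in Phase II and exploratory in Phase I (SAP 4.1), and it does not enter the 23/36 decision rule. Its Kaplan-Meier analysis is conditional on enough patients or responders. SAP 7 records that the study was terminated early and that many analyses may not be run.

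**What to change.** - In SAP 8.7.1.3, state that TTR is summarised descriptively in confirmed responders only (n, median, range).
- Delete Appendix B rows 2 to 4.
- Revise rows 1 and 5 together to say how a responder whose first response follows two consecutive missed assessments is handled.
- If an all-treated estimate is also wanted, specify the cumulative incidence of response in the full analysis set, with progression and death as competing events.

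The cost is SAP wording, with no new data and no change to sample size or to the decision rule.

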
 - To evaluate the safety and tolerability of HH2710 administered orally in patients with advanced tumors; - To identify the Maximum Tolerated Dose (MTD) and/or Recommended Phase II dose (RP2D). 	
 - Safety and Tolerability: The incidence, type, and severity of adverse events (AEs) assessed according to the National Cancer Institute-Common Terminology Criteria for Adverse Events (NCI-CTCAE) V5.0, physical examination findings, clinical laboratory values, vital signs and Electrocardiograms (ECGs); - The MTD, if any, and RP2D for HH2710 will be determined based on safety, tolerability, PK, preliminary efficacy, and other available data. 	
Phase II:	Phase II:	

 - To evaluate efficacy of HH2710 in patients with advanced tumors with MAPK signaling pathway genetic alterations, at the recommended phase 2 dose (RP2D). 	
 - Tumor objective response rate (ORR) based on RECIST v1.1. 	
Secondary		Refer to Section 10.5
Phase I:	Phase I:	

 - To characterize the pharmacokinetic profiles of HH2710 and selected metabolites when administered orally in patients with advanced tumors. 	
 - Peak plasma concentration (Cmax), peak time (tmax), area under the plasma concentration-time curve from time 0 to time (t) (AUC0-t), plasma elimination half-life (t1/2), plasma clearance rate constant (λ_z), apparent clearance (CL/F), apparent volume of distribution (Vz/F). 	

Objective	Endpoint	Analysis
Phase II	Phase II	

 - To evaluate the efficacy of HH2710 in advanced tumor patients with MAPK signaling pathway genetic alterations; - To evaluate the safety of HH2710. 	
 - Efficacy: The duration of response (DoR), progression-free survival (PFS), disease control rate (DCR), time to response (TTR), time to progression (TTP), and 1-year overall survival (OS) rate; - Safety: The incidence, type, and severity of adverse events (AEs) assessed according to the National Cancer Institute-Common Terminology Criteria for Adverse Events (NCI-CTCAE) V5.0, physical examination findings, clinical laboratory values, vital signs and Electrocardiograms (ECGs). 	
Exploratory	Phase I:	Refer to Section 10.6

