10.6.3 Secondary Efficacy Endpoint(s)

In Phase I, there is no secondary efficacy endpoints.

In Phase II, Kaplan-Meier method will be used to analyze the duration of response (DOR), the progression-free survival (PFS), time to response (TTR), time to progression (TTP) and 1-year overall survival (OS) rate for each tumor type and genetic mutation. If possible, a 95% of

confidence interval should be provided for each estimate. The point estimate and its 95% exact confidence interval (Clopper Pearson) will be used for analyzing DCR.

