8.12 Changes From Protocol-specified Analyses

1 year survival rate instead of 1 year overall survival time will be summarized in SAP.

Percentages will be presented to 1 decimal place unless otherwise specified in SAP.

For baseline characteristics, SAP will present Previous Anti-tumor Therapy Type: medication, surgery and radiotherapy instead of previous chemotherapy and previous immunotherapy.

Updated Safety Set to Safety Analysis Set and All-Treated Set to Full analysis set and keep the algorithm the same as protocol.

Members of the review committee will be internal and external to the sponsor.

Remove “Final Analysis section”. By default, primary analyses are final analysis.

Remove “Percentages will be rounded to the nearest whole number (zeroes are not displayed) with values of “< 1%” and “> 99%” shown as necessary for values falling near the boundaries” from general principles section.

9. Literature Citations / References

Clopper CJ and Pearson ES. The use of confidence or fiducial limits illustrated in the case of the binomial. *Biometrika.* 1934; 26(4):404-413.

Liu S, et al., Bayesian Optimal Interval Designs for Phase I/II Clinical Trials. *Journal of the Royal Statistical Society.* 2015, 64(3): 507-523

10. Appendices

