10.5 Appendix E Definitions

ORR

Objective response rate is defined as the percentage of patients who have at least one confirmed response of CR or PR defined by RECIST 1.1 prior to any evidence of progression.

DoR

Duration of response will be defined as the time from the date of first documented response, (that is subsequently confirmed) until date of documented progression or death in the absence of disease progression, the end of response should coincide with the date of progression or death from any cause used for the PFS endpoint. The time of the initial response will be defined as the latest of the dates contributing towards the first visit response of PR or CR.

DCR

Disease control rate is defined as the proportion of subjects with advanced tumors among whom achieve a best overall response CR/PR/SD after treatment with HH2710.

PFS

PFS is defined as the time from date of first dosing until the date of objective disease progression as defined by RECIST 1.1 or death (by any cause in the absence of progression) regardless of whether the subject withdraws from HH2710 treatment or receives another anticancer therapy prior to progression.

Overall Survival

Overall survival is defined as the interval between the date of first dose and the date of patient death due to any cause. Patients who have not died at the time of the statistical analysis will be censored at the time they were last known to be alive.

TTR

TTR is defined as the duration from the first day of study treatment until the first documented response (CR or PR).

TPP

TPP is defined as the duration from the first day of study treatment until the first documented progression (PD).

Baseline

For data analyses, baseline will be defined as the value measured on day 1 of the start of HH2710. The protocol specifies that all study procedures on day 1 should be completed before the initiation of HH2710 which will be the assumption in the analysis unless the time of the assessment is recorded. If a day 1 value is not available, the latest value before the day of the start of HH2710 may be used.

End of Treatment Date

The end of HH2710 therapy date is the date the decision was made to end investigational product reported on the end of investigational product administration CRF.

End of Study

For a subject: a subject ends the study when they die, consent is withdrawn, or they are lost to follow-up. The end of study date will be captured on the end of study CRF.

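### The SAP replaces the protocol's Kaplan-Meier estimate of 1-year overall survival with a binomial proportion, does not state the change, and gives no rule for patients censored before month 12

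*SAP*

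**What the plan says.** **Protocol.** The 1-year OS rate is a Phase II secondary endpoint (Table 3-1: "time to response (TTR), time to progression (TTP), and 1-year overall survival (OS) rate"). Section 10.6.3 has one Kaplan-Meier sentence covering DoR, PFS, TTR and, at its end, "time to progression (TTP) and 1-year overall survival (OS) rate for each tumor type and genetic mutation". The exact binomial method is assigned separately, and only to one endpoint: "The point estimate and its 95% exact confidence interval (Clopper Pearson) will be used for analyzing DCR".

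**SAP.** Section 8.7.1.3 leaves OS out of both of its Kaplan-Meier sentences. The second reads "For all the time-to-event endpoints (DoR, PFS, TTR and TTP), the survival curve will be estimated by the Kaplan-Meier estimate". OS is then paired with DCR: "DCR and 1-year overall survival (OS) rate will be estimated and analyzed by the same methods as those in ORR". The ORR method, in 8.7.1.2, is a rate "along with the 95% of confidence interval calculated by the Clopper-Pearson method". Appendix E nevertheless defines OS as a time from first dose, and patients not known to have died "will be censored at the time they were last known to be alive".

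**Declared changes.** The only entry on this endpoint in SAP 8.12 is "1 year survival rate instead of 1 year overall survival time will be summarized in SAP".

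**The concern.** The two documents name different estimators for the same endpoint, and the list of changes does not reveal it. The 8.12 entry contrasts a rate with a time, but the protocol already calls the endpoint a rate in its synopsis, Table 3-1, 10.5.2 and 10.6.3. A Kaplan-Meier value at month 12 is also a survival rate, so a reader cannot infer from the entry that a proportion will be used.

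The SAP is also incomplete on its own terms. A proportion needs a yes/no status at month 12 for each patient, whereas Appendix E produces a censored time. SAP 6.1 and 8.7 make all treated patients the efficacy population, and 8.1 rules out imputation. Nothing says whether a patient last known alive at, say, month 7 counts as alive, as not alive, or is left out. Two programmers could report different 1-year OS rates from the same data, and under non-informative censoring each of the three conventions is biased.

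**Working it through.** **Can censoring before month 12 occur?** It is not the scheduled norm: protocol 7.1.5.2 continues survival calls until 1 year after progression or new therapy. It is permitted in three ways:

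- Protocol 4.3 and SAP Appendix E end the study once at least 80% of Phase II patients have died, been lost or been followed for 12 months, so up to 20% may be none of these.
- Loss to follow-up at any time satisfies that rule.
- Protocol 4.3 lets survival follow-up be cut short if enrolment stops early.

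**Inputs.** The documents give no expected 1-year OS and no censoring rate, so there is no planned figure to reproduce. Assumed: exponential survival with 12-month survival S; a share f of patients has a potential censoring time uniform on 0 to 12 months; everyone else is followed past month 12. Cohort maxima of 36 (Cohorts 1 and 2) and 9 (Cohort 3) come from protocol 10.4.

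**Formulas** (censoring unrelated to prognosis)

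- Censored before month 12: c = f(1 − S)/(−ln S)
- Counted as not alive: (1 − f)S
- Counted as alive: (1 − f)S + c
- Excluded: (1 − f)S/(1 − c)

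At S = 0.50 and f = 0.20: c = 0.2 × 0.5/0.693 = 0.144; not alive 0.8 × 0.5 = 0.400; alive 0.400 + 0.144 = 0.544; excluded 0.400/0.856 = 0.467.

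The same formulas at S = 0.50 for other f:

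| f | Censored before month 12 | Not alive | Alive | Excluded |
|---|---|---|---|---|
| 5% | 3.6% | 47.5% | 51.1% | 49.3% |
| 10% | 7.2% | 45.0% | 52.2% | 48.5% |
| 20% | 14.4% | 40.0% | 54.4% | 46.7% |
| 30% | 21.6% | 35.0% | 56.6% | 44.7% |

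Simulation at n = 36 agrees at f = 10%, 20% and 30%. Over S = 0.30 to 0.60 and f = 10% to 30%, the bias is about −3 to −18 points (not alive), +2 to +9 (alive) and −1 to −5 (excluded). Kaplan-Meier stays within 0.1 point of the truth.

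**Coverage of the 95% interval**, simulated at S = 0.50, in the order not alive / alive / excluded:

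- n = 36, f = 20%: 84 / 95 / 96%; Kaplan-Meier (log-log) 95%
- n = 36, f = 10%: 94 / 97 / 97%
- n = 36, f = 5%: 97 / 97 / 97%
- n = 9, f = 20%: 92 / 95 / 98%; Kaplan-Meier 97%

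**If censoring depends on prognosis**, Kaplan-Meier is biased too. Take f = 20% and overall 12-month survival of 50%. If the potentially censored patients have twice the hazard of the others, the means are 44 / 56 / 50% against Kaplan-Meier 52%, so exclusion happens to be closest. With half the hazard they are 36 / 53 / 44% against 48%.

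**Worked cases**

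- *Nine patients*: deaths at months 2, 5 and 8; last known alive at months 3 and 7; four alive at month 12. Not alive 4/9 = 44%; alive 6/9 = 67%; excluded 4/7 = 57%. Kaplan-Meier 8/9 × 6/7 × 4/5 = 61%.
- *Thirty-six patients*: 7 deaths before month 6, 7 censored at month 6, 7 deaths in months 6 to 12, 15 alive at month 12. Not alive 15/36 = 41.7% (95% CI 25.5 to 59.2); alive 22/36 = 61.1% (43.5 to 76.9); excluded 15/29 = 51.7% (32.5 to 70.6). Kaplan-Meier 29/36 × 15/22 = 54.9% (35.5 to 70.7). The unstated rule alone moves the result by 61.1 − 41.7 = 19.4 points.

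**The case against.** The strongest reply concerns weight. SAP section 7 says the programme has stopped and many planned analyses may not be run. The documents report no Phase II enrolment, and the endpoint is secondary, descriptive and tied to no decision rule. This stands and limits the practical consequence, but it does not reconcile the two documents.

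Second, 8.12 does mention the endpoint, and its wording may have been meant to record the move away from a time-to-event analysis. Perhaps so, but it names neither estimator and misdescribes the protocol endpoint.

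Third, the SAP may be less ambiguous than it looks. The ORR method, an all-treated denominator and no imputation together suggest patients observed alive at month 12 divided by all treated. That is a reasonable inference, but the SAP does not state it, and under non-informative censoring it is the convention with the largest downward bias and the poorest coverage.

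Fourth, 20% potential early censoring is near the limit of the end-of-study rule, although early losses could add to it. With 5% to 10% the bias falls to between 1 and 5 points and coverage is 94% or better. This also stands: the size depends on follow-up that the documents do not predict.

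Finally, Kaplan-Meier can fail to give a usable interval in very small, heavily censored samples. That is true, and the reporting rule should provide for it.

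**Conclusion.** The SAP is wrong as written on this endpoint. It departs from protocol 10.6.3 without saying so, and it applies a method that cannot use the censoring rule in its own Appendix E. Only the OS half of the sentence is at fault; Clopper-Pearson for DCR agrees with the protocol.

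With every patient dead or followed to month 12, the point estimates coincide and nothing is lost. With early censoring unrelated to prognosis, the proportion is biased in expectation: downward if censored patients are counted as not alive or excluded, upward if counted as alive. In a single sample it can still equal Kaplan-Meier, for example under exclusion when all censoring precedes the first death. At an assumed 50% survival and 20% potential early censoring the bias is −10, +4 or −3 points, depending on the convention. These sizes rest on exponential survival and uniform censoring times. Kaplan-Meier's advantage rests on censoring being non-informative. The point should be corrected, but no trial decision depends on it.

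**What to change.** In SAP 8.7.1.3, take the 1-year OS rate out of the sentence on DCR and restore the protocol method: the Kaplan-Meier estimate at month 12 under the Appendix E censoring rule, with a 95% CI of a named type (for example log-log with Greenwood variance). Keep Clopper-Pearson for ORR and DCR. Also state:

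- the number of patients censored before month 12;
- that the estimate is reported as not estimable, with individual survival times listed, if nobody is at risk at month 12 and the last observation is censored;
- what is reported when the estimate is 0 or 1, for example Clopper-Pearson if nobody was censored before month 12, otherwise CI not estimable.

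If the sponsor prefers the proportion, 8.12 should name the change of estimator and say how patients of unknown status at month 12 are counted.

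**Cost.** The core change is one or two sentences; the procedure is already planned for PFS. At n = 36 and OS 50%, the mean log-log CI width is 31.5 points with complete follow-up and 33.4 with 20% potential early censoring; in the latter case the proportion gives 33.1 / 33.6 / 36.4 (not alive / alive / excluded). At true OS of 30/50/70%, no usable log-log CI arises in 8/1/6% of samples at n = 9 with 20% potential censoring, 23/9/11% at n = 9 with 50%, and 75/67/69% at n = 5 with 80%. That is why the not-estimable rule is needed.
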